10.4 Subjects Decision to Withdraw

Subjects have the right to withdraw from the study at any time and for any reason without prejudice to their future medical care by the physician or at the institution.

Withdrawal of consent for a study means that the subject does not wish to or is unable to continue further study participation. Subject data up to withdrawal of consent will be included in the analysis of the study, and where permitted, publicly available data can be included after withdrawal of consent. The Investigator is to discuss with the subject appropriate steps for withdrawal of their consent from the study.

11. Collection, Recording and Reporting of Safety Information and Product Complaints

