Immunoglobulin	
institutional review board	
IR (irinotecan) OX (oxaliplatin)	
interactive voice response system	
Kirsten rat sarkoma 2 viral oncogene homolog, gen of RAS family	

Product: Panitumumab (Vectibix®) Protocol Number: 20170734 POWER Date: 29 April 2019

Date: 29 April 2019 Page 9 of 64

Abbreviation or Term	Definition/Explanation	
LV	Leucovorin, folinic acid	
mCRC	metastatic colorectal cancer	
MedDRA	Medical dictionary for regulatory activities	
MRI	magnetic resonance imaging	
NRAS	neuroblastoma RAS viral oncogene homolog, gene of RAS family	
ORR	objective response rate	
OS	overall survival	
OTC	over the counter	
PET	positron emission tomography	
PFS	progression-free survival	
PP	percentage points	
QoL	quality of life	
RECIST	response evaluation criteria in solid tumours	
RR	response rate	
SAP	statistical analysis plan	
SmPC	summary of product characteristics	
TGFα	transforming growth factor-alpha	
TNM	tumour node metastasis	
WT	wild type	
VEGF	vascular endothelial growth factor	
VEGFR	vascular endothelial growth factor receptor	
5-FU	fluorouracil	
Baseline Visit	The date of start of 1st line chemotherapy and panitumumab	
Enrolment Visit	The date of informed consent signature	
End of Observation Visit	The visit at the end of Prospective Observation Period or the last visit before death or withdrawal of informed consent or lost to follow-up	
End of Study Visit	The visit at the end of Safety Follow-up or at the end of Prospective Observation Period if panitumumab was not administered in the last 4 weeks of observation	
Prospective Observation Period	Period between Enrolment and start of Safety Follow-up defined as 1) 15 months of continuous 1st line panitumumab plus chemotherapy treatment administration or 2) up to 15 months after stop of 1st line treatment without subsequent 2nd line treatment or 3) 1st line panitumumab plus chemotherapy until progression/start of 2nd line treatment or death or withdrawal of informed consent or loss-to follow-up, whichever occurs first	

Product: Panitumumab (Vectibix®) Protocol Number: 20170734 POWER Date: 29 April 2019

Date: 29 April 2019 Page 10 of 64

Abbreviation or Term	Definition/Explanation
Retrospective Period	Period between start of 1 st line panitumumab plus chemotherapy and enrolment

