8.3 Exploratory Objectives (if available)

9. Research Methods

This is an observational study and thus real world data will be extracted from medical files and collected prospectively.

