9.2.3 Subject/Healthcare Professional Eligibility

9.2.3.1 Inclusion Criteria

- I. Subject who received first infusion of panitumumab in combination with chemotherapy as 1st line treatment between 1 and 12 months before enrolment and who is continuing on treatment with panitumumab in combination with chemotherapy at the time of enrolment
- II. Subject with a record of WT RAS CRC diagnosis as per standard clinical practice
- III. Subject with metastatic carcinoma of the colon or rectum with at least one metastatic site recorded

Date: 29 April 2019 Page 26 of 64

IV. Subject with initially non resectable mCRC at the start of panitumumab plus chemotherapy treatment

- V. Subject who was diagnosed with a tumour, assessed by CT/MRI etc. prior to panitumumab plus chemotherapy initiation
- VI. Histologically or cytologically confirmed carcinoma of the colon or rectum as the primary site
- VII. Subject ≥ 18 years of age on the date of enrolment/ICF signature
- VIII. Subjects whose care will be managed primarily by the enrolling physician and/ or all records will be available from initiation of 1st line panitumumab plus chemotherapy treatment
- IX. Subject or subject's legally acceptable representative has provided informed consent

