9.2.7 End of Observation Visit

The End of Observation Visit is defined as a visit at completion of the 15-month observation period, or at the end of 1st line treatment; whichever occurs first. The End of Observation Visit is also defined as a last visit before death, withdrawal of consent, or lost to follow-up; whichever occurs first.

The following data will be collected at the End of Observation Visit:

- Adverse events: type and duration of AE; prophylaxis treatment for skin toxicity, occurrence of skin toxicity and details of skin toxicity management using FACT - EGFRI-18 QoL questionnaire (See Appendix F) if permitted in a country per local regulations.
- All other safety events with the exception of the protocol exempted events.
- Date and reason for ending study:
 - 15-month observation period reached (measured from the enrolment visit)
 - start of 2nd line treatment
 - death date and primary cause of death to be recorded
 - lost to follow-up
 - withdrawal of informed consent
- Tumour evaluations using all or any of the following methods: CT, MRI, PET, chest X rays, bone X rays, ultrasound assessments (any performed) or radio nuclear examinations
- Resection status as applicable.

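### Section 10.4 counts inability to continue as withdrawal of consent, so a subject who has revoked nothing may be censored while chart data could still be abstracted

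*Protocol*

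**What the plan says.** Section 10.4 is the only place that says what withdrawal means: "Withdrawal of consent for a study means that the subject does not wish to or is unable to continue further study participation". It then sets the data rule: "Subject data up to withdrawal of consent will be included in the analysis of the study", with the addition that "where permitted, publicly available data can be included after withdrawal of consent".

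Withdrawal also closes observation. In Section 2, the definition of the Prospective Observation Period ends with "death or withdrawal of informed consent or loss-to follow-up, whichever occurs first". Section 9.2.7 says: "The End of Observation Visit is also defined as a last visit before death, withdrawal of consent, or lost to follow-up; whichever occurs first". Its list of reasons for ending study has five entries: 15 months reached, start of 2nd line treatment, death, lost to follow-up, and "withdrawal of informed consent". Inability to participate has no entry of its own.

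On data sources, the opening of Section 9 says that "real world data will be extracted from medical files and collected prospectively". Section 9.4 refers to medical files and routine clinic visits, and Section 9.3.2 adds no procedures beyond routine practice. Inclusion criterion VIII asks that care be managed primarily by the enrolling physician and/or that "all records will be available from initiation of 1st line panitumumab plus chemotherapy treatment". Criterion IX accepts consent from a legally acceptable representative.

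Death and disease progression are analysed by Kaplan-Meier (Section 9.7.2.4), and missing data are not imputed (Section 9.7.2.2).

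**The concern.** Being unable to continue is not a decision about the use of one's data. A subject who can no longer take part has refused nothing, and the study draws largely on records that exist anyway. By classing that subject as withdrawn, Section 10.4 gives sites a reason to stop abstraction where consent still stands.

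Two things are at stake. First, Kaplan-Meier assumes that censored subjects carry the same future risk as those still observed. In metastatic colorectal cancer, inability to participate plausibly follows deterioration. If it does, the censored subjects are at higher risk than average and the estimated probabilities of death and progression are pulled down. Second, the reported number of consent withdrawals would mix refusals with inability and could not be read as either.

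**Working it through.** **1. The rules side by side.**
- Section 10.4: inability counts as withdrawal of consent.
- Section 2 and Section 9.2.7: withdrawal ends observation.
- Section 10.4: data count up to that point; afterwards only public data, where permitted.
- Section 9.2.7: there is no separate code for inability, so the Section 10.4 definition leads to the withdrawal code. Lost to follow-up is the only other listed reason that could fit.
- Sections 9.7.2.2 and 9.7.2.4: Kaplan-Meier without imputation.

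Read together, these rules allow a consented subject to be censored at the onset of inability. No other section overrides the definition.

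**2. The protocol's own precision figure.** The abstract (Section 4) states a 95% half-width of at most 4 percentage points for a proportion with 600 subjects. At p = 0.5 the half-width is 1.96 × √(0.25/600) = 4.0 points, so the figure reproduces. It applies to a simple proportion and is not a benchmark for Kaplan-Meier bias.

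**3. Illustration of direction and possible size.** Every input here is an assumption, because the protocol gives no rate of inability, death or progression.
- Event times are exponential, all subjects are followed from time zero, and the horizon is 15 months.
- The true 15-month event probability m is 30% or 60%.
- A share f of events is pre-empted by a cut-off 1 month earlier, and nothing is recovered afterwards.

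If a share f of events is replaced by censoring at nearly the same time, the estimated hazard falls to about (1 − f) of the true hazard. The estimate is then approximately 1 − (1 − m)^(1 − f). For m = 30% and f = 10%: 1 − 0.70^0.90 = 27.5%. A simulation of 400,000 subjects gives slightly higher values, because cutting a month early also shrinks the risk set sooner:

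| True m | f | Formula | Simulated Kaplan-Meier | Shortfall (m minus simulated) |
|---|---|---|---|---|
| 30% | 5% | 28.7% | 28.8% | 1.2 points |
| 30% | 10% | 27.5% | 27.6% | 2.4 points |
| 30% | 20% | 24.8% | 24.9% | 5.1 points |
| 60% | 5% | 58.1% | 58.3% | 1.7 points |
| 60% | 10% | 56.2% | 56.4% | 3.6 points |
| 60% | 20% | 52.0% | 52.4% | 7.6 points |

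In numbers of subjects, m = 30% and f = 10% mean 0.30 × 0.10 × 600 = 18 subjects whose event within 15 months is pre-empted; f = 20% means 36.

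**4. Comparator.** With censoring of 10% or 20% of subjects unrelated to prognosis, the same simulation returns 30.0% for m = 30% and 60.1% for m = 60%. The shortfall therefore comes entirely from the assumed link between inability and prognosis.

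**The case against.** The rest of Section 10.4 describes an active choice. Its heading speaks of the subject's decision, it opens with the right to withdraw, and it has the investigator discuss the steps with the subject. With routine care only, in-patient centres included (Section 9.2.2) and representatives able to consent, a sick subject need not be unable to participate. This makes misclassification less likely, but it does not change the one sentence that defines the term.

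A site might instead code such a subject as lost to follow-up, with the same censoring. That is correct, and it means the fix must cover both codes. Continued access to records is also not guaranteed: criterion VIII is an and/or condition, and care may move elsewhere.

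A reader might infer that death and progression *are* understated, or that subjects too ill to attend *are* cut off. The documents do not support either as fact. The text says only that the subject is unable, and it gives no reason for the inability and no frequency.

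A reader might also set a 5-point shortfall against the 4-point half-width and conclude that bias exceeds sampling error. That fails for three reasons. The share f is invented. Observation already ends at progression or start of 2nd line treatment (Section 2), so many later deaths are missed for a different reason that the illustration does not model. Public data may recover some deaths, although they are unlikely to supply progression. Nor is there a basis for saying that 2nd line choices are lost in any number, since the documents do not show how many such subjects would have started 2nd line treatment.

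Finally, Section 9.9.1.1 anticipates bias from missing data in general. It does not address loss created by a definition in the protocol itself.

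**Conclusion.** The point holds as a defect of definition with a conditional consequence. Section 10.4 merges inability with revoked consent, and the protocol's other rules turn that into an end of observation for a subject who may still be fully consented. If inability tracks clinical decline and sites apply the definition as written, the Kaplan-Meier estimates of death and progression may be understated. The size cannot be derived from the documents and could be small. Under the stated assumptions, with 5% to 20% of events pre-empted, the shortfall is about 1 to 8 points; it is zero if inability is unrelated to prognosis. The outcomes affected are secondary and the study is descriptive, so this is an inexpensive correction worth making and not a threat to the study's main purpose.

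**What to change.** - **Section 10.4:** limit withdrawal of consent to an explicit revocation by the subject or the legally acceptable representative, deleting the words *or is unable to*. Add that a subject who cannot participate but has not revoked consent stays in the study. Progression, 2nd line start and death are then abstracted from available records, where consent and local rules allow, until another end-of-observation event occurs.
- **Section 9.2.7 and the eCRF:** record inability to participate as a visit status. It should not be entered as withdrawal of consent or, while records remain accessible, as lost to follow-up.

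The cost is one revised definition with a sentence added, one eCRF status option, and a little more chart abstraction for a few subjects. No extra visits, procedures or subjects are needed.

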11.1 Definition of Safety Events

11.1.1 Adverse Events

An adverse event is any untoward medical occurrence in a subject administered a pharmaceutical product(s) irrespective of a causal relationship with this treatment.

An adverse event can therefore be any unfavourable and unintended sign (including an abnormal laboratory finding, for example), symptom, or disease temporally associated with the use of a product(s), whether or not considered related to the product(s). The definition of an adverse event includes:

- Worsening of a pre-existing condition or underlying disease
- Events associated with the discontinuation of the use of a product(s), (eg, appearance of new symptoms)

It is the Investigator's responsibility to evaluate whether an adverse event is related to an Amgen product prior to reporting the adverse event to Amgen.

There is no requirement to monitor study subjects for adverse events after end of study. However, if adverse events are reported, the investigator is to report

Date: 29 April 2019 Page 42 of 64

them to Amgen or to the local health authorities.

11.1.2 Serious Adverse Events

A serious adverse event is any adverse event as defined above that meets at least one of the following serious criteria:

- is fatal
- is life threatening (places the subject at immediate risk of death)
- requires in-patient hospitalization or prolongation of existing hospitalization
- results in persistent or significant disability/incapacity
- is a congenital anomaly/birth defect
- is an "other medically important serious events" that does not meet any of the above criteria

A hospitalization meeting the regulatory definition for "serious" is any in-patient hospital admission that includes a minimum of an overnight stay in a healthcare facility.

"Other medically important serious events" refer to important medical events that may not be immediately life threatening or result in death or hospitalization, but may jeopardize the subject or may require intervention to prevent one of the other outcomes listed in the definition above. Examples of such events could include allergic bronchospasm, convulsions, and blood dyscrasias, drug-induced liver injury, events that necessitate an emergency room visit, out-patient surgery, or other events that require other urgent intervention.

11.1.3 Other Safety Findings

Other Safety Findings (regardless of association with an adverse event) include:

- Medication errors, overdose, whether accidental or intentional, misuse, or abuse, involving an Amgen product,
- Pregnancy and lactation exposure,
- Transmission of infectious agents,
- Reports of uses outside the terms for authorized use of the product including offlabel use,
- Occupational exposure,
- Any lack or loss of intended effect of the product(s).

11.1.4 Product Complaints

Product Complaints include any written, electronic or oral communication that alleges deficiencies related to the identity, quality, durability, reliability, safety, effectiveness, or performance of a product or device after it is released for distribution to market or clinic by either Amgen or by distributors and partners for whom Amgen manufactures the

Date: 29 April 2019 Page 43 of 64

material. This includes any drug(s), device(s) or combination products provisioned and/or repackaged/modified by Amgen. Drug(s) or device(s) includes investigational product.

11.1.5 Safety Collection, Recording and Submission to Amgen Requirements

This study is analysing secondary data from sources including, but not limited to, administrative claims, electronic health records (EHR) and medical charts. The safety outcomes that are listed in section 9.3.2 will be documented on medical chart review forms and analysed in this study.

These will be reported in aggregate in the final OR study report as Tables, Figures and Listings.

See section 9.3.2 for safety outcomes and definitions. Submission of safety outcomes as individual safety reports to Amgen is not required. Safety events suspected to be related to any medicinal product should be reported to the local authority in line with the local country requirements.

11.1.5.1 Prospective Observational Period

This study is collecting information from subjects ambidirectionally (retrospectively-prospectively). All safety events (adverse events, product complaints, and other safety findings) considered to have occurred following subject exposure to panitumumab will be collected from signing of informed consent form with the exception of the protocol exempted events listed in appendix G to final study contact. The Investigator is responsible for ensuring that all safety events they become aware of during study period, are recorded in the subject's appropriate study documentation. Those safety events which are considered serious must also be submitted as individual safety reports to Amgen Safety via the applicable Amgen Safety Reporting Form (paper or electronic form) within 1 business day of Investigator awareness. Non-serious Adverse Events (AEs) must be reported in an expeditious manner, not to exceed 15 calendars days of Investigator awareness.

If the electronic data capture (EDC) system is unavailable to the site staff, the adverse event which is considered serious must still be reported to Amgen within 1 business day of Investigator's awareness using the paper Adverse Event Contingency Report Form. For EDC studies where the first notification of an Adverse Event is reported to Amgen via the Adverse Event Contingency Report Form, the data must be entered into the EDC system when the system is again available. Non-serious Adverse Events (AEs) must be

Date: 29 April 2019 Page 44 of 64

reported in an expeditious manner, not to exceed 15 calendars days of Investigator awareness.

See Appendix B and Appendix D Additional Safety Reporting Information. The Investigator may be asked to provide additional information for any event submitted, which may include a discharge summary or extracts from the medical record. Information provided about the event must be consistent with information recorded in the study documentation where safety data may also be recorded.

Protocol Exempted Events

Non-serious adverse events that are anticipated to occur in this study population because they are known adverse reactions to chemotherapy or are known to occur in the context of the underlying disease are not planned to be collected in this study. Exempted events are those adverse events that are listed as adverse reactions for panitumumab treatment in the European Medicinal agency's summary of product characteristics and not relevant for any of the study objectives.

Safety data on panitumumab are routine clinical care setting worldwide, panitumumab has been marketed for more than 11 years worldwide. In this single arm observational study, where only approximately 600 exposed patients will be enrolled, it is very unlikely that this will create any such substantial new pharmacovigilance data when adverse events not considered by the Investigator to have a causal relationship with panitumumab are collected. A list of all events and corresponding MedDRA preferred terms that are not to be collected in the study is provided in Appendix G.

Other safety findings and product complaints (see definitions in Section 11.1.3 for Other Safety Findings and 11.1.4 for Product complaints) are required to be collected and reported to Amgen in this study.

If any of the exempted events are serious or have a fatal outcome, they should be considered a serious adverse event and must be collected and reported individually within 1 business day of Investigator awareness.

All safety information that is not specified in this section including all fatal events are to be collected and submitted to Amgen within the specified time frame.

Protocol exempted events and safety events that are suspected to be related to any medicinal product other than panitumumab should be reported to the local authority in line with the local country requirements.

See Appendix B. Sample Safety Reporting Form(s) and Appendix C. Pregnancy and Lactation Notification Worksheets. The Investigator may be asked to provide additional

Date: 29 April 2019 Page 45 of 64

information for any event submitted, which may include a discharge summary or extracts from the medical record. Information provided about the event must be consistent with information recorded in the study documentation where safety data may also be recorded.

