8.2 Secondary Objectives

- To assess the response to 1st line treatment.
- To explore the relationship between death and/or disease progression and subject / country characteristics.
- To characterize the group of subjects with ETS outcome (if available).
- To assess incidence of adverse drug reactions (ADR).

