Safety Follow-up will last approximately 30 days after the start of 2nd line treatment, or after 15 months of observation if panitumumab was administered in the last 4 weeks of observation, whichever occurs first, except for death, withdrawal of consent or lost to follow-up. If a subject receives panitumumab in combination with chemotherapy for 15 months, then 30 days of Safety Follow-up will be the 16th month of observation.

Date: 29 April 2019 Page 23 of 64

Table 2. Objectives and Outcomes

Objectives	Outcomes	Exposure variables
Primary		
To obtain characteristics of subjects with WT RAS non resectable mCRC receiving panitumumab in combination with chemotherapy as a 1 st line treatment.	 Demographics Disease history, including location of tumour (left vs. right side) Current status of disease 	Country Total
To describe the patterns of treatment , including 1 st and 2 nd line therapies.	 1st line treatment Any changes during 1st line treatment, including dose, infusion schedule, and reasons for changes Type of progression leading to 2nd line choice Type of 2nd line treatment (type of anticancer therapy) 	 Country Location of tumour (left vs. right side) Oxaliplatin-based chemotherapy Irinotecan-based chemotherapy Total
	 Dose, schedule and reason for treatment selection Subsequent treatment line/approach 	D 1

Page 1 of 2

Date: 29 April 2019 Page 24 of 64

Objectives	Outcomes	Exposure variables
Secondary		
To assess the response to 1 st line treatment described by: the relationship between death, disease progression, ETS (if available), and subject characteristics with the particular interest in tumour location	 Death Disease Progression Response rate Rate of conversion to resectable mCRC Tumour markers: CEA and CA 19.9 Early tumour shrinkage (if available) 	Country Location of tumour (levs. right side) Current disease status Oxaliplatin-based chemotherapy Irinotecan-based chemotherapy Total
To assess incidence of adverse drug reactions (ADR) events (general)	ADR reports: type and duration of ADR incident	Country Total
Exploratory (if available)		

Date: 29 April 2019 Page 25 of 64

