9.3.2 Outcome Assessment

Primary outcomes

As primary outcomes the following data will be collected:

- characteristics of subjects with WT RAS non resectable mCRC receiving panitumumab in combination with chemotherapy as a 1st line treatment, including:
 - demographics: age, sex
 - targeted medical history: type of primary tumour and the date of diagnosis; site of primary tumour: rectum vs colon, right vs left colon; surgical procedures; lymph nodes: number and involvement; TNM stage; adjuvant chemotherapy, including regimen if applicable; sites of metastatic disease: liver, lung, other;
 - current status of mCRC: ECOG performance status, RECIST criteria (if available), ETS at week 8 (if available)
- pattern of treatment composed of:
 - 1st line treatment: agents and doses at baseline, any changes during
 1st line treatment, including dose, infusion schedule, and reasons for changes
 - 2nd line treatment: type of progression leading to 2nd line choice, type of 2nd line anti-cancer therapy, dose, schedule and reason for treatment selection

Secondary outcomes

In the secondary outcomes the following data will be gathered:

- Response to 1st line treatment measured as:
 - Death
 - Disease Progression
 - response rate (RR)
 - rate of conversion to resectable mCRC
 - tumour markers: CEA and CA 19.9
 - ETS (if available as per clinical practice) at week 8 measured by all or any of the following methods: CT, MRI, PET in comparison to the baseline.
- Safety assessments:
 - ADR reports related to panitumumab treatment
 - type and duration of ADR incident

Exploratory outcome

CCI

Date: 29 April 2019 Page 32 of 64

In study sites routinely performing biomarkers assessment in liquid biopsies, disease biomarkers information will be collected as per local regulations.

Since this is an observational study, all tests will be performed in line with routine clinical practice and no additional procedures are posed by the protocol.

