9.7.3 Analysis of Safety Outcomes

Number of subjects with serious and non-serious ADRs leading to discontinuation of panitumumab and serious ADRs associated with fatal outcomes will be tabulated by system organ class and preferred term.

Measures of skin toxicity management (FACT- EGFRI-18 QoL questionnaire (See Appendix F) if allowed per local regulations), type of measures, duration, severity of skin toxicity, and type of treatment will be summarized.

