Appendix G. Protocol Exempted Events

MedDRA System Organ Class	MedDRA Prefferd Term(s)
Infections and infestations	Conjunctivitis Urinary tract infection Localised infection
Blood and lymphatic system	Eye infection Anaemia
disorders	Leucopenia
Immune system disorders	Hypersensitivity
Metabolism and nutrition disorders	Hypocalcaemia Dehydration Hyperglycaemia Hypophosphataemia
Psychiatric disorders	Insomnia
1 Sychiatric disorders	Anxiety
Nervous system disorders	Headache Dizziness
Eye disorders	Blepharitis Lacrimation increased Ocular hyperaemia Dry eye Eye pruritus
Cardiac disorders	Tachycardia Cyanosis
Vascular disorders	Deep vein thrombosis Hypotension Hypertension Flushing
Respiratory, thoracic and mediastinal disorders	Dyspnoea Cough Pulmonary embolism Epistaxis Interstitial lung disease ³ Bronchospasm Nasal dryness
Gastrointestinal disorders	Nausea Vomiting Abdominal pain Constipation Rectal haemorrhage Dry mouth Dyspepsia Aphthous ulcer Cheilitis Gastro-oesophageal reflux disease Chapped lips Dry lips
Musculoskeletal and connective tissue disorders	Back pain Pain in extremity

Product: Panitumumab (Vectibix®) Protocol Number: 20170734 POWER Date: 29 April 2019

Date: 29 April 2019 Page 64 of 64

General disorders and	Fatigue
administration site conditions	Pyrexia
	Asthenia
	Mucosal inflammation
	Oedema peripheral
	Chest pain
	Pain
	Chills

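### The ADR-incidence objective is general, but non-serious occurrences of 55 listed panitumumab reactions are exempt from collection, and the collection instructions contradict one another

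*Protocol*

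**What the plan says.** **Objective and outcome.** Protocol Section 8.2 gives the secondary safety objective as "To assess incidence of adverse drug reactions (ADR"), with no restriction. Table 2 repeats it as "To assess incidence of adverse drug reactions (ADR) events (general"), with type and duration as the outcome. Section 9.3.2 defines the safety outcome as "ADR reports related to panitumumab treatment".

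**Exemption.** Section 11.1.5.1 collects safety events from consent "with the exception of the protocol exempted events listed in appendix G to final study contact". It defines these events as follows: "Exempted events are those adverse events that are listed as adverse reactions for panitumumab treatment" in the European product information, on the further condition that they have no bearing on any study objective. Serious or fatal occurrences are still collected. The justification offered is that little new safety information would arise "when adverse events not considered by the Investigator to have a causal relationship with panitumumab are collected". Appendix G lists terms by system organ class, for example "Nausea Vomiting Abdominal pain Constipation", with no reference to causality.

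**Other collection instructions.** Section 9.2.6 asks monthly for ADR events by type and duration and mentions no exemption. Section 9.2.5 takes panitumumab side effects into the medical history, also without one. Section 11.1.5 says the Section 9.3.2 safety outcomes will be documented and analysed. Sections 9.2.7 and 9.2.8 ask for adverse events as one item and attach the exemption to a separate item covering all other safety events.

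**Analysis.** Section 9.7.3 tabulates, among other things, "Number of subjects with serious and non-serious ADRs leading to discontinuation of panitumumab".

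**The concern.** The study sets out to estimate how often panitumumab reactions occur, then selects events for non-collection because they are known panitumumab reactions. An event that is never recorded cannot be restored by a later analysis plan, so this is not a detail that can wait for one.

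The collection sections also disagree. One site may follow 11.1.5.1 and leave out a non-serious Appendix G event. Another may follow 9.2.6 and enter it. The resulting counts would be neither complete nor consistently limited to serious cases, and differences between countries, one of the planned breakdowns in Table 2, could reflect reading of the protocol rather than tolerability. At stake are the incidence figures for the listed terms and any summary that includes them, in a study whose results Section 7.2 expects may support reimbursement assessments.

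**Working it through.** **Step 1: the exemption against the protocol's own statements.**
- *Its condition.* A listed panitumumab reaction is exempt only if irrelevant to every objective. With general ADR incidence as an objective and panitumumab-related ADRs as the outcome, an event judged to be a panitumumab reaction cannot meet that condition.
- *Its rationale.* The justification concerns events the investigator considers unrelated to panitumumab. The rule has no causality test, so it also removes related events.
- *Its description.* The same section first describes the exempted events as expected from chemotherapy or the underlying disease, then as listed panitumumab reactions. These are different sets.
- *Other sections.* 9.2.5, 9.2.6 and 11.1.5 collect panitumumab side effects or ADRs without the exemption. In 9.2.7 and 9.2.8 its reach is unclear.

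**Step 2: size of the list (count of Appendix G).** Infections 4, blood 2, immune 1, metabolism 4, psychiatric 2, nervous system 2, eye 5, cardiac 2, vascular 4, respiratory 7, gastrointestinal 12, musculoskeletal 2, general 8. The sum is 55 distinct preferred terms in 13 classes. There is no skin-disorder class and no rash term.

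**Step 3: the plan's precision figure, as a yardstick.** The Abstract promises a 95% half-width of no more than 4 percentage points (pp) with 600 subjects. At p = 0.5, 1.96 × √(0.25/600) = 0.0400, so the figure is reproduced.

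**Step 4: what can be estimated.** Let p be the true proportion of subjects with a related event of a given term, and s the share of them whose event is serious. If every site follows 11.1.5.1:

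observed = p × s, shortfall = p × (1 − s).

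If a share r of the non-serious cases is recorded anyway, because some sites follow 9.2.6:

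observed = p × [s + (1 − s) × r], shortfall = p × (1 − s) × (1 − r).

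**Step 5: illustration.** The protocol gives none of p, s or r for these terms, so the values below are assumptions. With r = 0 and half-width = 1.96 × √(p(1 − p)/600):

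| Assumed p | Assumed s | Observed | Shortfall | Half-width at p |
|---|---|---|---|---|
| 40% | 2% to 10% | 0.8% to 4.0% | 39.2 to 36.0 pp | 3.9 pp |
| 20% | 2% to 10% | 0.4% to 2.0% | 19.6 to 18.0 pp | 3.2 pp |
| 5% | 50% to 80% | 2.5% to 4.0% | 2.5 to 1.0 pp | 1.7 pp |

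The last row stands for terms that may often be serious, such as pulmonary embolism or deep vein thrombosis. Uneven recording widens the range. At p = 20% and s = 5%, the shortfall is 0.20 × 0.95 × (1 − r), which is 19.0 pp at r = 0 and zero at r = 1. The direction is fixed, but the documents do not determine the size.

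**The case against.** The best defence is that the exemption is a deliberate and disclosed choice. Panitumumab has been marketed for more than 11 years, the study is descriptive with no hypothesis, only one secondary objective is touched, and Appendix G states openly what is not collected. Leaving out some non-serious events is legitimate. That stands, but it does not justify keeping a general ADR objective, and the stated reason covers only unrelated events.

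The defence also limits how far the point can be taken. A reader might infer any of the following, and the documents do not support them.
- *That the listed reactions would appear at close to zero.* Serious cases are collected, some terms may often be serious, and sites following 9.2.6 may enter non-serious cases.
- *That a non-serious listed event leading to discontinuation would be absent from the data altogether.* Section 9.2.6 records reasons for dose changes and for stopping treatment, and Section 9.7.2.4 summarises reasons for cessation. What is missing is any statement that such an event is also recorded as an ADR, with the type and duration the objective needs.
- *That known panitumumab reactions in general are lost.* Skin toxicity, which Section 7.1 calls the most common reaction to this class, is not in Appendix G and is a focus of data collection.
- *That a specific overall ADR rate is biased.* Section 9.7.3 names tables only for ADRs leading to discontinuation and serious ADRs with fatal outcome. Section 11.1.5 does promise aggregate reporting of the 9.3.2 outcomes, but an overall total is not specified. In a per-subject total, subjects with a recorded skin reaction would already be counted.

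**Conclusion.** The contradiction is in the text and should be resolved. For the 55 Appendix G terms, Section 11.1.5.1 permits estimation of serious incidence only, while the objective claims ADR incidence in general. Because other sections ask for ADRs without the exemption, non-serious cases would probably be recorded by some sites and not by others.

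Incidence for these terms would be understated, as would any total or 9.7.3 discontinuation table that includes them. For a common and mostly non-serious term the shortfall could be several times the 4 pp precision target; for a rarer and often serious term it could be a point or two. Both statements rest on assumed incidences and serious shares, and no single percentage can be given for the list. The primary objective and the skin toxicity data are not affected.

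**What to change.** Choose one of two routes.

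1. **Match the exemption to its rationale.** In 11.1.5.1 and Appendix G, exempt a listed non-serious event only when the investigator does not consider it related to panitumumab. Cost: an amendment and some extra event entries at visits that already ask for ADRs.
2. **Keep the list and narrow the objective.** In 8.2 and Table 2, restate it as the incidence of serious ADRs and of non-exempted non-serious ADRs, including skin toxicity. Report no overall ADR total, and mark the 55 terms in the tables as not collected if non-serious. Cost: wording only, with a narrower safety claim.

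Under either route, bring 9.2.5 to 9.2.8 and 11.1.5 into line with the exemption so that every site receives the same instruction. State that any ADR leading to discontinuation of panitumumab is recorded as an ADR, listed or not, so that the 9.7.3 table is complete.
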